9. STUDY PROCEDURES
 - 9.1. PRE- AND ABLATION PROCEDURE
 - 9.1.1. PRE-PROCEDURE
 - 9.1.2. PRE-PROCEDURE MEDICATION MANAGEMENT
 - 9.1.3. ABLATION PROCEDURAL DETAILS
 - 9.2. POST-PROCEDURE
 - 9.2.1. POST-PROCEDURE FOLLOW-UP
 - 9.2.2. POST-PROCEDURE MEDICATION MANAGEMENT
 - 9.2.3. ICD PROGRAMMING
 - 9.3. SAFETY
 - 9.3.1. INITIAL INTERIM AND FUTILITY ANALYSES
 - 9.3.2. CLINICAL EVENTS COMMITTEE
 - 9.3.3. DATA SAFETY MONITORING BOARD
 - 9.4. RISKS
 - 9.4.1. SERIOUS ADVERSE EVENTS
 - 9.4.2. UNANTICIPATED SERIOUS ADVERSE EVENTS
 - 9.4.3. UNANTICIPATED ADVERSE DEVICE EFFECTS
 - 9.4.4. UNANTICIPATED PROBLEMS
 - 9.4.5. EVENT RECORDING
 - 9.4.6. CAUSALITY

- 9.4.7. REPORTING OF SERIOUS ADVERSE EVENTS AND UNANTICIPATED ADVERSE DEVICE EFFECTS
- 9.4.8. REPORTING OF UNANTICIPATED PROBLEMS
- 9.4.9. DCC REPORTING TO FDA

- 10. STATISTICAL ANALYSIS PLAN
 - 10.1. STUDY DESIGN
 - 10.2. PRIMARY OBJECTIVES
 - 10.3. PRIMARY EFFECTIVENESS ENDPOINT
 - 10.4. PRIMARY SAFETY OBJECTIVE
 - 10.5. SECONDARY ENDPOINTS
 - 10.6. POWER AND SAMPLE SIZE
 - 10.7. INTERIM MONITORING GUIDELINES
 - 10.8. STATISTICAL ANALYSIS
 - 10.9. PRIMARY SAFETY ANALYSIS
- 11. ETHICAL AND REGULATORY CONSIDERATIONS
 - 11.1. STUDY DATA COLLECTION PROCESSING
 - 11.2. CONFIDENTIALITY
 - 11.3. DEVIATIONS FROM PROTOCOL
 - 11.4. WITHDRAWAL OF SUBJECTS
 - 11.5. ECONOMIC IMPACT ON SUBJECTS
- 12. STUDY MANAGEMENT
 - 12.1. RISK TO SUBJECTS
 - 12.2. POTENTIAL BENEFITS TO SUBJECTS
 - 12.3. ROLE OF DATA COORDINATING CENTER
 - 12.4. ONSITE MONITORING
 - 12.5. MAINTAINING RECORDS
 - 12.6. SITE RECORD RETENTION POLICY
 - 12.7. INSTITUTIONAL REVIEW BOARD / ETHICS COMMITTEE INFORMATION
- 13. DATA HANDLING

REFERENCES

PROTOCOL SUMMARY

Title:	REnal Sympathetic denervation to sUpprEss Ventricular Tachyarrhythmias in ICD Recipients (RESCUE)
Objective:	The objective of this trial is to determine the efficacy and safety of adjunctive catheter-based renal sympathetic denervation (RSDN) in the primary prevention of ICD therapy in patients with ischemic or non-ischemic ventricular dysfunction, who are to receive an ICD for either i) secondary prevention, or ii) primary prevention + inducible VT by programmed ventricular stimulation at the time of ICD implantation. These patients will be randomized to ICD alone or ICD + RSDN.
Design:	This study is a prospective, multicenter, single-blinded, randomized (1:1) control trial evaluating the effectiveness of RSDN in the primary prevention of ICD therapy in patients with ischemic or non-ischemic ventricular dysfunction who are to receive an ICD for either i) secondary prevention, or ii) primary prevention + inducible VT by programmed ventricular stimulation at the time of ICD implantation. These patients will be randomized to ICD alone or ICD + RSDN. Subjects will only be eligible for this study if they are \geq 18 years of age and have a history of structural heart disease (post-MI, dilated cardiomyopathy, sarcoid myopathy, hypertrophic cardiomyopathy, etc.), and are planned for ICD implantation for: i. Secondary prevention (e.g.: VT/VF arrest, sustained VT, syncope/inducible VT) ii. Primary prevention + inducible MMVT during induction via ICD lead testing. In addition, eligible patients will have accessible renal vasculature (as determined by renal angiography).
	The patient will be blinded to the results of randomization. Once randomized, study group subjects will undergo a strategy of catheter-based renal sympathetic denervation + ICD implantation (if not already present). Control patients will receive standard ICD implantation alone (if not already present). Follow-up will be conducted in regular intervals over a 12-month period.
Enrollment:	Total: 462 subjects (231 control group, 231 study group)
	An interim safety analysis will be performed after the first 50 subjects (25 control group, 25 study group) have completed their 6-month follow-up visit.
Clinical Sites:	
• Icahn School of Medicine at Mount Sinai• Homolka Hospital, Prague, Czech Republic• Heart Center U SV. Anny Hospital, Brno, Czech Republic• Massachusetts General Hospital• Regional Cardiology, Sacramento, California• Medical University of South Carolina• Florida Hospital, Orlando, Florida

	
 • Other Sites TBD
Time Course:	Enrollment: Over 4 years
Subject Description:	Eligible subjects include those \geq 18 years of age with a history of structural heart disease (post-MI, dilated cardiomyopathy, sarcoid myopathy, hypertrophic cardiomyopathy, etc.), who are planned for ICD implantation for: i. Secondary prevention (e.g.: VT/VF arrest, sustained VT, syncope/inducible VT) ii. Primary prevention + inducible MMVT during induction via ICD lead testing. iii. Primary prevention + fragmented QRS complex on 12-lead ECG. In addition, eligible patients will have accessible renal vasculature (determined by renal angiography).
Study Group:	In addition to ICD implantation, the subjects in this group will undergo catheter-based renal sympathetic denervation.
Control Group:	Subjects in the control group will undergo standard ICD implantation alone (if not already present).
Primary Endpoint:	Time to first event requiring any ICD therapy (appropriate or inappropriate) or Incessant VT (VT occurring below the ICD rate cut-off); this will be assessed in the on-treatment patient cohort.
Secondary Endpoints:	
 1. Appropriate ICD therapy assessed in the full intention-to-treat patient cohort 2. Inappropriate ICD therapy 3. Number of Hospitalizations for Cardiovascular Causes. 4. Total VT burden (Number of episodes). 5. All-Cause Mortality. 6. The occurrence of ICD storm, defined as \geq3 appropriate shock therapies within 24 hours. 7. Differences in BUN/creatinine measurements. 8. Procedure related adverse events including, but not limited to hematomas, pseudoaneurysms and renal artery stenosis. 9. Development of orthostatic hypotension 10. 30-day Major Complication Rate defined as death, stroke, MI or any other serious adverse events related to the treatment or procedure within the first 30 days or through hospital discharge (whichever is longer);
Primary Analytical Analysis:	Intent to treat analysis
Secondary Analytical Analysis:	Per protocol analysis

Principal Investigator: [name].
Icahn School of Medicine at Mount Sinai
[name]
[name], USA

Site, Monitoring, and Data Management Center Electrophysiology Clinical Research Group
Icahn School of Medicine at Mount Sinai
[name]
[name], USA

Data Safety and Monitoring Board: Chair: [name] (general cardiologist)
[name] (electrophysiologist)
[name] (general cardiologist)
[name] (nephrologist)
[name] (biostatistician)

8. TBD	

2 STUDY OBJECTIVE

The goal of this trial is to determine the efficacy and safety of adjunctive catheter-based renal sympathetic denervation (RSDN) in the primary prevention of ICD therapy in patients with ischemic or non-ischemic ventricular dysfunction, who are to receive an ICD for either i) secondary prevention, or ii) primary prevention + inducible VT by programmed ventricular stimulation at the time of ICD implantation. These patients will be randomized to ICD alone or ICD + RSDN. The proposed study is a prospective, multicenter, single-blind, randomized control trial.

3 INTRODUCTION, RATIONALE

Sudden cardiac death (SCD), defined as an unexpected death from a cardiac cause occurring within \leq 1 hour of the onset of symptoms, accounts for 300,000 to 400,000 deaths in the United States annually, or 5.6% of annual mortality.¹⁻³ SCD is most commonly caused by ventricular tachyarrhythmias, including ventricular tachycardia (VT). Several therapies exist for the prevention of VT, including implantable cardioverter-defibrillator therapy (ICD), anti-arrhythmic drug therapy (AAD), and the use of catheter based ablation.

Current guidelines recommend the use of implantable cardioverter-defibrillator (ICD) as therapy to prevent SCD in patients who have survived a prior cardiac arrest due to unstable VT or who have had a previous episode of spontaneous sustained VT.⁴ Several trials have demonstrated the efficacy of ICD therapy in preventing SCD.^{5,6} The MADIT II trial, a randomized trial of patients with prior myocardial infarction and left ventricular ejection fraction \leq 30%, demonstrated a 31%

reduction in the relative risk of death in the defibrillator group.⁶ However, ICD therapy does not prevent VT, and a significant proportion of patients may still experience appropriate shocks. In the Antiarrhythmics Versus Implantable Defibrillators (AVID) Trial, 60% of patients had ≥ 1 appropriate ICD therapy for VT/VF during follow-up (31±13 months), and the first arrhythmia resulting in a shock during follow up was frequently identified as VT (63%). Unfortunately, these ICD shocks are associated with both a significant reduction in quality of life and increased mortality. In a study examining quality of life in patients who had received ICD shocks, at 5.5 years post ICD implantation 19% of patients demonstrated signs of post-traumatic stress disorder.⁷ In the MADIT II trial, patients who experienced VT/VF had an increased risk of death, with a hazard ratio of 2.5.⁶ Thus, while ICDs have a clear overall mortality benefit in patients with a reduced ejection fraction, the ICD shocks themselves clearly reduce the quality-of-life of these patients and may have a negative impact on their longevity.

Antiarrhythmic drugs (AADs) are another therapy available for the prevention of VT, but unfortunately they have little effect on ventricular arrhythmia recurrence, and may increase mortality when used in high-risk patients. In the OPTIC trial, 412 patients who had an ICD implanted within 21 days for inducible or spontaneously occurring VT/VF were randomized to either amiodarone plus beta-blocker, sotalol alone, or beta-blocker alone. Although patients in the amiodarone plus beta blocker group were less likely to receive shocks (HR, 0.27; 95% CI, 0.14-0.52; $P<.001$), shocks still occurred in 10.3% of these patients. In addition, serious adverse effects associated with amiodarone resulted in study drug discontinuation in 18.2% of patients at 1 year.⁸

More recently, catheter ablation has emerged as a new option for the primary prevention of ICD shocks. Current guidelines recommend catheter ablation for symptomatic sustained monomorphic VT, including VT terminated by an ICD, that recurs despite AAD therapy or when AADs are not tolerated. In addition, ablation is indicated for control of VT storm refractory to drug therapy when there is a suspected trigger than can be targeted for ablation.⁹ The Substrate Mapping and Ablation in Sinus Rhythm to Halt Ventricular Tachycardia Study (SMASH-VT) randomized patients with a history of myocardial infarction who underwent defibrillator implantation for spontaneous VT or VF, to either defibrillator implantation alone or defibrillator implantation plus substrate-based catheter ablation. In patients who underwent defibrillator implantation alone 33% received ICD therapies (anti-tachycardia pacing or shocks), compared to 12% in patients who received defibrillator implantation plus substrate-based catheter ablation (Hazard ratio in the ablation group, 0.35; 95% confidence interval, 0.15 to 0.78, $P=0.007$).¹⁰ Similar results were seen in another multicenter randomized trial of similar design, VTACH. Despite the efficacy of VT ablation in these trials, this therapy is limited by: i) the complexity of the procedure requiring significant operator experience, ii) the duration of the procedure in these patients with ventricular dysfunction, iii) the potential risk of the procedure (despite the fact that no significant complications were seen in SMASH-VT and VTACH), and iv) SMASH-VT and VTACH only included the post-MI patient population since the substrate ablation approach is less applicable to patients with non-ischemic cardiomyopathy.

Thus, anti-arrhythmic drugs and catheter ablation each have limitations as adjunctive therapy in patients at risk for ICD shocks; new strategies are needed. One strategy under investigation is renal sympathetic denervation (RSDN). Recently, RSDN has been developed as a therapy to treat hypertension in patients resistant to anti-hypertensive drug therapy. In the Catheter-Based Renal Sympathetic Denervation for Resistant Hypertension (Symplicity HTN-1) Trial: a multicenter safety and proof-of-principle cohort study, 45 patients with a mean office blood pressure of 177/101 mm Hg (SD 20/15), (mean 4.7 antihypertensive medications) underwent renal sympathetic denervation with radiofrequency based catheter ablation. After the procedure, these patients experienced a mean decrease in office blood pressure of -27/-17 mm Hg at 12 months, as

well as a 47% reduction in renal noradrenaline spillover.¹¹ In the Renal Sympathetic Denervation in Patients with Treatment-Resistant Hypertension (Symplicity HTN-2) Trial, a multi-center prospective trial that randomized 106 patients to RSDN or medical management, at 6 months, 84% of patients who underwent renal denervation had a reduction in systolic blood pressure of 10 mm Hg or more, compared with 35% of controls ($p<0.0001$).

RSDN is thought to decrease blood pressure by a number of mechanisms including its ability to favorably affect whole body norepinephrine spillover and decrease central sympathetic tone. Indeed, RSDN has been shown to reduce whole body norepinephrine spillover by 42%, and efferent muscle sympathetic nerve activity by 66%.¹² Interestingly, increased catecholamine and sympathetic activity are both important factors in the development of ventricular arrhythmias.¹³⁻¹⁸ In addition, chronic hypertension is believed to mediate pathogenesis and progression of cardiac arrhythmias via its remodeling effects on cardiac anatomy through the renin-angiotensin-aldosterone system.¹⁹

Despite significant advances in the management of ventricular arrhythmias through the use of ICD therapy, AADs, and catheter-based ablation strategies, considerable challenges remain. The optimal method for the prevention of ICD shocks remains unclear. RSDN may be an effective tool for preventing ventricular arrhythmias, and associated ICD therapies, by reducing central sympathetic tone, catecholamine levels, and the renin-angiotensin-aldosterone system. Although RSDN has been shown to reduce the recurrence of VT in a case report of 2 patients suffering from electrical storm, to date no large prospective randomized study has evaluated the impact of RSDN in the primary prevention of ICD therapy in patients with ischemic or non-ischemic ventricular dysfunction. Also of note, there is data suggesting that RSDN may even decrease the rate of supraventricular arrhythmias such as atrial fibrillation. Thus, RESCUE will specifically evaluate the safety and efficacy of RSDN in the prevention of ICD therapy in patients with ventricular dysfunction who are to receive an ICD for either secondary prevention, or primary prevention if they have inducible VT by programmed ventricular stimulation at the time of ICD implantation. As an alternative to inducible VT, we will also utilize a non-invasive predictor of sudden cardiac death - fragmented QRS complex by 12-lead ECG - as a criterion to identify candidates for RSDN. Fragmented QRS, which is defined by the presence of notching in the R or S wave or the presence of a second R wave in two contiguous leads, has been recognized as a risk predictor for all-cause mortality with relative risk of 1.71 (95% CI 1.02-2.85) and for sudden cardiac death with relative risk 2.20 (95% CI 1.05-4.62) in a recent meta-analysis of studies involving patients with coronary disease or non-ischemic cardiomyopathy.²⁸

3.1 INITIAL PILOT DATA:

In an initial pilot study, an irrigated radiofrequency catheter (Celsius Thermocool F-Curve RF catheter, Biosense-Webster, Inc., Diamond Bar, California) was used in 20 patients with ischemic or non-ischemic ventricular dysfunction, who were scheduled to receive an ICD for either i) secondary prevention, or ii) primary prevention + inducible VT by programmed ventricular stimulation at the time of ICD implantation ([name], unpublished observation). Although we have favorable single-operator, single-center safety data in another RSDN trial, preliminary review of the six-month renal ultrasound data provided a higher than expected event rate of renal artery stenosis. As such, the protocol has been amended to allow for the use of a dedicated renal sympathetic denervation catheter system: the Vessix™ Renal Denervation System (Boston Scientific, Quincy, Massachusetts).

4. SCHEDULE OF TREATMENT AND TESTS:

TABLE 1:

	Baseline	Procedure*	Discharge	1, 6,12,18,24,36 months**
Type of visit	Office	Hospital		Office
Informed Consent	X			
Brief History & Physical	X			X
Blood Laboratory Testing: CBC, Electrolytes, BUN/ Creatinine, BNP	X			X (6, 12, 24, 36m)
Blood for Renal Hormones (OPTIONAL*)	X			X (12m)
TTE	X			X (12 m)
Renal Angiography		X		
Ultrasound or MR/ CT Angiography				X (6 m)
Randomization		X		
Renal Sympathetic Denervation		X		
ICD Interrogation	X			X
EKG	X			X (12m)
Office BP Measurements (including orthostatic BPs)	X			X
Medications	X		X	X
Adverse Events		X	X	X

* Hormonal measurements are optional in cases where the cost would be prohibitively burdensome to patients or hospital/clinic facilities are not available to allow for their measurement.

** - Visit windows – 1 Month (\pm 14 days); 6, 12, 18, 24, 36 Months (\pm 30 days)

5. ENDPOINTS:

5.1 PRIMARY ENDPOINT:

The following primary endpoint will be assessed: Time to first event requiring any ICD therapy (appropriate or inappropriate) or Incessant VT (VT occurring below the ICD rate cut-off); this will be assessed in the on-treatment patient cohort. An event requiring ICD therapy is defined as an anti-tachycardia pacing (ATP) or shock therapy. The null hypothesis of principal interest is that there will be no difference between the two treatment arms in the time to first event requiring any ICD therapy (appropriate or inappropriate) or Incessant VT in patients randomized to ICD implantation with a single renal sympathetic denervation procedure compared to patients randomized to ICD implantation alone.

5.2 SECONDARY ENDPOINTS:

The following secondary endpoints will be assessed:

1. Appropriate ICD therapy assessed in the full intention-to-treat patient cohort
2. Inappropriate ICD therapy
3. Number of Hospitalizations for Cardiovascular Causes.
4. Total VT burden (Number of episodes).
5. All-Cause Mortality.
6. The occurrence of ICD storm, defined as ≥ 3 appropriate shock therapies within 24 hours.
7. Differences in BUN/creatinine measurements.
8. Procedure related adverse events including, but not limited to hematomas, pseudoaneurysms and renal artery stenosis.
9. Development of orthostatic hypotension
10. 30-day Major Complication Rate defined as death, stroke, MI or any other serious adverse events related to the treatment or procedure within the first 30 days or through hospital discharge (whichever is longer)

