9.3.2 CLINICAL EVENTS COMMITTEE

A separate Clinical Events Committee (CEC) composed of 2 independent cardiologists/ electrophysiologists will adjudicate all ICD events in this study.

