10.6 POWER AND SAMPLE SIZE

Power for this study was determined based on the following operating characteristics: (a) two sided type I error fixed at 0.0492, assuming one interim analysis, (b) 85% power, (c) minimum follow-up of 18 months, (d) 18-months event rate in the ICD alone group of 19% (e) expected 18-month relative rate reduction in the ICD + RSDN group of $\geq 40\%$, accrual period of 48 months and non-uniform accrual.

Under the above assumptions it is estimated that 70 events (or 462 patients) will be required to detect a relative decrease in the relative event rate reduction requiring any ICD therapy $\geq 40\%$ in the ICD + RSDN compared to the ICD alone group (19% vs. 11.4%) (Lachin, 1981).

Lost to Follow Up: The term "lost to follow-up" is used to define an individual who has withdrawn consent to be in the study or who can no longer be located or assessed. Such individuals represent those for whom primary outcome assessment is no longer possible. Since the primary outcome will be assessed by interrogating the ICD and since patients come back to

the hospital for regular check we do not anticipate a high rate of lost to follow-up. The estimated sample size accounts for 5% attrition due to withdrawal of consent.

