10.7 INTERIM MONITORING GUIDELINES

The objectives of interim monitoring are to (1) monitor for safety, (2) track participant accrual rates, and (3) monitor the primary and secondary outcomes for early evidence of efficacy, harm or futility. To accomplish this, summaries of data quality, accrual, adherence, distribution of baseline factors, toxicity, study endpoints and other analyses as requested will be prepared for review by the Data Safety Monitoring Committee (DSMB).

The primary outcome of the trial, rate of first event requiring any ICD therapy, is the basis for formal interim analysis plan that follows. One interim analysis and one final analysis are planned for this trial, for a total of 2 analyses. These analyses will be performed when 0.5 and 1.0 fraction of the total number of events will have been observed. Since this study will have a target number of events of 70, we will have approximately 35 events observed between each analysis time.

We will use an alpha-spending O'Brien-Fleming sequential procedure as a guideline for decision making. At the interim analysis the value of the test statistic will be compared with the alpha spending function critical values. The two alpha values will be set at 0.0054 at the interim analysis and 0.0492 at the final analysis, which equate to critical values of 2.782 and 1.967 respectively. This monitoring plan maintains the overall type I error at 0.05, given one interim analysis.

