10.8 STATISTICAL ANALYSIS

The primary analysis will be an intent-to-treat analysis that will include all randomized participants regardless of treatment actually received or follow-up schedule.

Point Estimation and Interval Estimation: We will report maximum likelihood estimates for point estimation. For routine reporting, two-sided 95% confidence intervals for all parameters will be prepared.

Disposition of Participants and Baseline Comparisons: Summaries of all participants randomized and the number who complete visits at 30-days, and every 6 months after the day of randomization will be provided for each treatment group. The treatment groups will be compared at baseline with respect to demographics, baseline measurements related to efficacy and baseline measurements related to safety.

Univariate Analysis: All outcome measures will be described in a univariate analysis. For continuous variables means and standard deviations will be calculated. For discrete and dichotomous variables we will use contingency tables.

Analysis of Primary Endpoint: The primary endpoint of this study is defined time to first event requiring any ICD therapy (appropriate or inappropriate) or Incessant VT (VT occurring below the ICD rate cut-off); this will be assessed in the on-treatment patient cohort. An event requiring ICD therapy is defined as an anti-tachycardia pacing (ATP) or shock therapy. Time to event will be estimated using Kaplan-Meier curves. Survival time will be defined as the time (in months) between randomization and the occurrence of first ICD therapy. To compare the ICD+ RSDN arm with the ICD alone arm we will use a stratified log-rank statistic (using the stratification variables from the randomization procedure). A Cox proportional hazards model with treatment and other important prognostic factors as covariates will be used for the multivariate analysis of the times to first ICD therapy. Risk ratios and their 95% confidence intervals will be computed. Patients will be included in the analysis as censored if they are alive and free of ICD events at the end of the 18-month follow-up period. Although we do not anticipate interactions between treatment and stratification factors, formal tests for interactions will be assessed using proportional hazards models. A formal test of proportional hazards will assess the significance of

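### The incessant-VT component of the primary endpoint is defined by rate alone, while Sections 10.7 and 10.8 as worded would not count it at all

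*Combined protocol and SAP*

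**What the plan says.** The Protocol Summary and Sections 5.1, 10.3 and 10.8 all describe a time-to-first-event composite with two components.

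- **ICD therapy.** This is operational: "An event requiring ICD therapy is defined as an anti-tachycardia pacing (ATP) or shock therapy".
- **Incessant VT.** The only definition is the parenthesis in "Incessant VT (VT occurring below the ICD rate cut-off"), the same in all four places.

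Other sections bear on how the second component would be recorded and analysed:

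- Section 9.2.3 sets a VT zone of 175-195 bpm and a monitor zone of 130-170 bpm. It ties neither to the endpoint.
- Section 9.2.1 has VT episodes, ATP and shocks documented at every visit. Table 1 and Section 9.2.1 schedule one follow-up EKG, at 12 months.
- Section 9.3.2 says the Clinical Events Committee "will adjudicate all ICD events in this study". It gives no criteria for incessant VT.
- Section 10.6 assumes an "18-months event rate in the ICD alone group of 19"%, against 11.4% with denervation.
- Section 10.7 names the outcome for formal monitoring as "rate of first event requiring any ICD therapy".
- Section 10.8 restates the composite and then says: "Survival time will be defined as the time (in months) between randomization and the occurrence of first ICD therapy".

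**The concern.** The parenthesis describes slow VT. Nothing in the plan makes the word incessant operational: there is no duration, episode count, symptom, termination or intervention criterion. The authors did set such criteria elsewhere, since ICD storm requires at least three "appropriate shock therapies within 24 hours".

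Two analysts following the plan could therefore build different primary datasets. One would count any recorded VT below the cut-off. The other, following the survival-time sentence, would count none. The same ambiguity affects when the interim analysis falls due, at about 35 of 70 events.

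If slow VT is counted and denervation affects it less than it affects treated VT, the treatment contrast is diluted. Ascertainment is also uneven. The programming table shows no zone below 130 bpm, so finding VT there depends on an ECG or other recording outside the device. Only the patient is stated to be blinded, and Section 9.1.3 says that the operating physician knows the allocation.

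**Working it through.** **1. The sections side by side.** Two hypothetical patients show the conflict.

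| Patient | Composite read literally (Summary, 5.1, 10.3, 10.8) | Survival-time sentence (10.8) and outcome in 10.7 |
|---|---|---|
| Self-ending VT at 150 bpm in the monitor log, ATP at a later date | Event on the date of the slow VT | Event on the date of the ATP |
| Continuous VT at 120 bpm, no device therapy | Event, if someone documents it | No event |

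A third reader could give incessant its usual clinical sense and exclude the first patient's slow episode, but the plan supplies no threshold for doing so.

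**2. The plan's own effect size.** From Section 10.6, 19% × (1 − 0.40) = 11.4%, which reproduces. With exponential times the hazard ratio is ln(0.886)/ln(0.81) = 0.574.

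**3. Dilution on the 18-month risk scale.** The documents give no slow-VT rate, so q below is an assumption. It is the 18-month probability of a qualifying slow VT, equal in both arms, independent of ICD therapy, unaffected by denervation and additional to the 19% and 11.4%. The composite risk is 1 − (1 − p)(1 − q).

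| q | Control, p = 0.19 | Denervation, p = 0.114 | Relative reduction |
|---|---|---|---|
| 0 | 19.0% | 11.4% | 40% |
| 1% | 1 − 0.81 × 0.99 = 19.8% | 1 − 0.886 × 0.99 = 12.3% | 38% |
| 2% | 1 − 0.81 × 0.98 = 20.6% | 1 − 0.886 × 0.98 = 13.2% | 36% |
| 5% | 23.1% | 15.8% | 31% |
| 10% | 27.1% | 20.3% | 25% |
| 20% | 35.2% | 29.1% | 17% |

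**4. The same assumption on the hazard scale.** The diluted hazard ratio is [ln(0.886) + ln(1 − q)] / [ln(0.81) + ln(1 − q)]. Section 10.6 gives 85% power and a "two sided type I error fixed at 0.0492, assuming one interim analysis", so z = 1.967 and 1.036. Schoenfeld's formula for 1:1 allocation is D = 4(1.967 + 1.036)² / (ln HR)². Power is Φ(½√D × |ln HR| − 1.967), with D now the events expected from 462 patients. That expected count assumes uniform accrual over 48 months, follow-up of at least 18 and at most 36 months, and no dropout; the plan says that accrual is non-uniform but gives no shape.

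| q | Hazard ratio | Events for 85% power | Events expected | Power |
|---|---|---|---|---|
| 0 | 0.574 | 118 | 118.4 | 85% |
| 1% | 0.594 | 133 | 124.5 | 83% |
| 2% | 0.612 | 150 | 130.6 | 80% |
| 5% | 0.658 | 206 | 148.6 | 72% |
| 10% | 0.716 | 324 | 177.5 | 60% |

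The 118 events in the first row differ from the 70 stated in Section 10.6. The stated number matches the expected 18-month count, 462 × (0.19 + 0.114)/2 = 70.2. That is a separate matter, and the present point does not depend on it.

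**The case against.** The strongest reply is that incessant already points away from brief runs. On that view the parenthesis only explains why such VT is listed separately: it is below the cut-off, so no therapy marks it. The committee could then exclude brief episodes. This is a fair reading, but it is not a written rule, and the committee has no criterion to apply beyond rate.

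Several stronger conclusions are tempting, and the documents do not support them.

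- *Incessant VT is half of the endpoint.* It is one of two named components. No share of events is given.
- *A run of a few seconds will count the same as a shock.* It could count. No monitor-zone detection time is legible in Section 9.2.3, possibly because the table was damaged in extraction, so it is not established that such a run would be logged. Under the survival-time sentence it would not count.
- *The component bypasses adjudication.* The committee's remit covers ICD events, which can include device-logged slow VT. The gap concerns VT that the device does not record.
- *Counting slow VT censors later therapy.* A component event is an event, not censoring. Later therapy leaves the primary analysis but is still captured: appropriate and inappropriate therapy and total VT burden are secondary endpoints.
- *Follow-up staff know the allocation.* The plan states this only for the operating physician and is silent on follow-up staff.
- *The 19% excludes incessant VT.* Section 10.6 first calls it simply an event rate. The ICD-therapy wording in the next sentence may be shorthand for the whole composite. If 19% and 40% already refer to the composite, the dilution in the tables does not arise.

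The dilution figures also rest wholly on assumed rates, and at 1% to 2% the loss is small. The protocol's rationale is that denervation suppresses ventricular arrhythmia, so a null effect on slow VT is the unfavourable end of the range.

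**Conclusion.** The concern holds in this form. The stated definition turns on rate alone and, applied literally, can classify a self-ending slow VT as a first primary event. Sections 10.7 and 10.8 contain sentences under which incessant VT never counts. This goes beyond missing detail, because the plan gives rules that lead to different event dates for the same patient.

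The size is unknown. Assumed 18-month slow-VT rates of 1% to 20% take the relative reduction from 40% to between about 38% and 17%. In the accrual scenario shown, rates of 1% to 10% take power from 85% to between 83% and 60%. Both ranges assume equal rates in the two arms, independence from ICD therapy, no effect of denervation on slow VT, and a 19% that does not already include it. If denervation also reduces slow VT, the dilution is smaller. The case for correcting the text rests on the wording and not on these figures.

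**What to change.** Before any primary events are classified:

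1. In the Protocol Summary and Sections 5.1, 10.3 and 10.8, add to the incessant-VT definition a minimum duration or a need for intervention to terminate the episode, documented on a stored electrogram or ECG. The sponsor should choose and justify the threshold; 30 seconds is only an example. Any duration threshold will still admit some self-ending episodes just above it, which is why it needs a stated justification.
2. State that shorter runs count only toward the existing secondary endpoint of total VT burden.
3. Rewrite the survival-time and censoring sentences in Section 10.8, and the outcome named in Section 10.7, so that they refer to the full composite.
4. Extend Section 9.3.2 so that the existing committee adjudicates all suspected incessant VT, whether or not the device recorded it, as well as all ICD therapies.

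The cost is protocol and SAP wording, slightly fewer primary events than under the literal definition, and a few more episodes for the committee.
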